### 2. STUDY DESIGN

### 2.1. Synopsis of Study Design

This was a prospective, randomized, double-blind study. Subjects who completed the 6-month Treatment Period in the main study (18-OBE2109-002 - Edelweiss 2) were invited to enter the present extension study. Month 6 visit of the main study was a decision point for Subjects to either end treatment and enter a post-treatment follow up (part of the main study), or to opt for a 6-month treatment extension.

The extension study started at the Month 6 visit of the main study. Subjects were required to sign a specific informed consent form (ICF) for this extension study. Only subjects who completed the full 6-month Treatment Period in the main study and met the inclusion criteria were eligible for entry in the extension study.

All subjects received once daily linzagolix 75 mg alone (with ABT placebo) or 200 mg combined with ABT for 6 months. Subjects who received placebo during the main study were randomized in a 1:1 ratio to either linzagolix 75 mg alone (with ABT placebo) or linzagolix 200 mg with ABT. Subjects who received active treatment during the main study continued with the same treatment.

Linzagolix/placebo tablets were provided in monthly treatment kits, packaged, labelled and administered in the same manner to protect the blinded nature of the trial.

ABT/placebo treatments were supplied as 3-monthly kits, packaged, labelled and administered in the same manner to protect the blinded nature of the trial.

After end of treatment in the extension study (6-month Treatment Period: from Month 6 to Month 12), subjects entered a post-treatment Follow-Up Period of 6 months with no investigational medicinal product (IMP).

The total duration of the present extension study was to be 12 months.

Sponsor:	ObsEva		
Protocol:	19-OBE2109-00	5	
Document Version No.:	1.0	Document Date:	18-MAY-2021

A schematic of the study design is shown in Figure 1.

\* At the end of the 6-month follow-up period, subjects with a BMD decrease from baseline of >1.5% for lumbar spine and/or >2.5% for total hip compared to main study baseline will have an additional DXA scan 6 months later.

Figure 1: Study design

CRS-BS-TP-000005 V 1.0

Sponsor:	ObsEva		
Protocol:	19-OBE2109-00	5	
Document Version No.:	1.0	Document Date:	18-MAY-2021

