#### 4.2.11. Baseline Definitions

The baseline will be described in two ways:

- Main Baseline, defined in the Statistical Analysis Plan of the main study and calculated according to first dose of IMP taken during the main Study.
- Second Baseline (named Baseline 2), defined as the last assessment before the first active dose of IMP during the extension study. The baseline 2 will be calculated only for the subjects who are in the placebo arm (actual arm) in the main study.

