#### 4.8.4. Laboratory Data

Clinical laboratory values will be expressed using conventional SI units.

Hematology, coagulation parameters, chemistry and lipids were assessed at screening and at each visit during the extension treatment period (from M7 to M12), as well as at the M1 ExtFU and M3 ExtFU visits.

E2, progesterone (P4) and LH were assessed at each visit during the extension treatment period (from M6 to M12), as well as at M1 ExtFU and M3 ExtFU visits.

Serum levels of sex hormone-binding globulin (SHBG) were assessed on Month 6, Month 9 and Month 12 visits.

Blood samples were to be analyzed by the central laboratory. Due to the covid-19 situation, some samples may be collected by local laboratories.

For Hematology, coagulation parameters, chemistry and lipids, the actual value, change from baseline and change from baseline 2 (only for the subjects who are in the placebo arm in the main study) will be summarized for each visit for each treatment group. In the event of repeated values, the last non-missing value per study day/time will be used.

Evaluation of shifts for changes from baseline and for changes from baseline 2 (only for the subjects who are in the placebo arm in the main study) to all visits according to the normal ranges with categories "Low", "Normal", "High" and according to normal/abnormal/abnormal clinically significant information collected otherwise, will be provided.

For Liver Function Test (LFT) parameters (ALT, AST, ALP, total bilirubin, direct bilirubin, indirect bilirubin, GGT, LDH, albumin and Creatine Kinase), evaluation of shifts for changes from baseline will be extended by the worst (highest) on-treatment value (including unscheduled assessments) according to the normal ranges with categories "Low", "Normal", "High" will be provided.

For the lipid panel (Triglycerides, HDL, LDL, Total Cholesterol, LDL/HDL ratio), the percent change from baseline and the percent change from baseline 2 (only for the subjects who are in the placebo arm in the main study) to each on-study visit will also be summarized.

For serum levels of P4, SHBG and LH, only the actual values at each time point will be summarized. Note: in the event of repeated values, the last non-missing value per study day/time will be used.

Note that no serum levels of E2 is measured for subjects in extension study due to the early termination study.

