- Table 14.4.3.5 Coagulation Parameters Shifts from Baseline 2\* based on Clinical Findings from Month 7 up to Month 6 Extension Follow-up Extension Safety Analysis Set subset of subjects who are in the placebo arm (actual arm) in the main study
- Table 14.4.4.1 Chemistry Parameters by Visit from Month 7 up to Month 6 Extension Followup – Extension Safety Analysis Set See shell for Table 14.4.2.1.
- Table 14.4.4.2 Chemistry Parameters Shifts from Baseline Based on Clinical Findings from Month 7 up to Month 6 Extension Follow-up – Extension Safety Analysis Set
- Table 14.4.4.3 Chemistry Parameters Shifts from Baseline 2\* based on Clinical Findings from Month 7 up to Month 6 Extension Follow-up Extension Safety Analysis Set subset of subjects who are in the placebo arm (actual arm) in the main study
- Table 14.4.4 Chemistry Parameters Shifts from Baseline Based on Normal Ranges from Month 7 up to Month 6 Extension Follow-up – Extension Safety Analysis Set
- Table 14.4.4.5 Chemistry Parameters Shifts from Baseline 2\* based on Clinical Findings from Month 7 up to Month 6 Extension Follow-up Extension Safety Analysis Set subset of subjects who are in the placebo arm (actual arm) in the main study
- Table 14.4.5.1 Lipids by Visit from Month 7 up to Month 6 Extension Follow-up Extension Safety Analysis Set See shell for Table 14.4.2.1.

Sponsor:	ObsEva			
Protocol:	19-OBE2109-005			
Document Version No.:	1.0	Document Date:	18-MAY-2021	

- Table 14.4.5.2 Lipids LDL and HDL Categories by Visit from Month 7 up to Month 6 Extension Follow-up – Extension Safety Analysis Set
- Table 14.4.5.3 Lipids Shifts from Baseline Based on LDL Categories from Month 7 up to Month 6 Extension Follow-up – Extension Safety Analysis Set
- Table 14.4.5.5 Lipids Shifts from Baseline 2\* Based on LDL Categories from Month 7 up to Month 6 Extension Follow-up – Extension Safety Analysis Set – subset of subjects who are in the placebo arm (actual arm) in the main study
- Table 14.4.5.6 Lipids Shifts from Baseline Based on Triglycerides Categories from Month 7 up to Month 6 Extension Follow-up Extension Safety Analysis Set
- Table 14.4.5.7 Lipids Shifts from Baseline 2\* Based on Triglycerides Categories from Month 7 up to Month 6 Extension Follow-up – Extension Safety Analysis Set – subset of subjects who are in the placebo arm (actual arm) in the main study

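### The worst on-treatment liver-test shift is specified from the main-study baseline only, so some women who switched from placebo would be misclassified, in either direction

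*SAP*

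**What the plan says.** SAP 4.8.4 (Laboratory Data) sets out several laboratory summaries in sequence.

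- By-visit Low/Normal/High shifts: "Evaluation of shifts for changes from baseline and for changes from baseline 2", the latter for women in the main-study placebo arm.
- Worst liver-test value: "evaluation of shifts for changes from baseline will be extended by the worst (highest) on-treatment value (including unscheduled assessments", classified Low/Normal/High. Baseline 2 is not mentioned.
- Lipids, in the next paragraph: "the percent change from baseline and the percent change from baseline 2". The LDL and triglyceride category shifts also name both.

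SAP 4.2.11 separates the two reference points. The Main Baseline is "calculated according to first dose of IMP taken during the main Study". Baseline 2 is "defined as the last assessment before the first active dose of IMP during the extension study" and exists only for women whose actual main-study arm was placebo. SAP 2.1 explains why the distinction matters: "Subjects who received placebo during the main study were randomized in a 1:1 ratio to either linzagolix 75 mg alone" or to 200 mg with add-back therapy, so their first active dose comes at Month 6.

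Appendix B (SAP 7.2) lists by-visit chemistry shift tables but no worst-value liver-test table for either baseline. Tables 14.4.4.3 and 14.4.4.5 are both Baseline 2 chemistry shifts titled by clinical findings. The only chemistry shift titled by normal ranges is from the main baseline.

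**The concern.** For the two Placebo / linzagolix groups, the main baseline precedes six months of placebo. A shift from that point to the worst value on linzagolix mixes what happened on placebo with what happened on drug. In the continuing groups the main baseline directly precedes linzagolix, so there is no placebo interval to mix in.

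The SAP now concentrates on safety (SAP 1.2 and 5). Transaminase rises have been observed with this drug (Protocol 5.5.3 and 5.7) and carry discontinuation rules. The women switching from placebo are the only ones whose first exposure falls inside this study. The worst-value shift is also the one summary that explicitly includes unscheduled measurements, so it is where a transient peak would appear. If its starting point is not the pre-drug value, a reader cannot tell from the table whether a given woman's elevation began on linzagolix.

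**Working it through.** The plan states no figure on this point, so the check is a comparison of classifications, followed by an illustration of scale.

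**Step 1. Classify the possible histories of a woman who switched from placebo** (definitions from SAP 4.2.11 and 4.8.4).

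| Main baseline | Month 6, end of placebo | Worst value on linzagolix | Shift from main baseline | Shift from Baseline 2 |
|---|---|---|---|---|
| Normal | High | High | Normal to High | High to High |
| High | Normal | High | High to High | Normal to High |
| Normal | Normal | High | Normal to High | Normal to High |
| Normal | Normal (earlier placebo rise resolved) | Normal | Normal to Normal | Normal to Normal |

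Row 1 is charged to linzagolix although it began on placebo. Row 2 is a rise on linzagolix from a normal pre-drug value, and it is not counted. Rows 3 and 4 agree under both baselines.

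A fifth history depends on a missing definition: Normal at main baseline, High at Month 6, Normal at every later visit. From main baseline this is Normal to Normal if the window opens after the first extension dose, but Normal to High if the Month 6 pre-dose sample counts. SAP 4.8.4 does not define on-treatment. SAP 4.2.12 starts the extension treatment period at Month 6, yet puts Month 6 assessments in the main study for by-visit summaries.

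**Step 2. Does the choice of baseline bias the rate?** Assumptions, none of them in the documents: standard normal values with equal correlation between all visits, no drug effect, no trend, upper limit of normal at the 97.5th percentile, six extension values, 2,000,000 simulated women per setting.

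| Correlation | Normal to High, main baseline | Normal to High, Baseline 2 | Share of main-baseline shifts already High at Month 6 |
|---|---|---|---|
| 0.4 | 10.1% | 10.1% | 9.3% |
| 0.5 | 9.0% | 9.0% | 11.2% |
| 0.6 | 7.7% | 7.7% | 13.5% |
| 0.7 | 6.4% | 6.4% | 16.1% |
| 0.8 | 4.9% | 4.9% | 19.5% |

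The rates match by symmetry: row 1 and row 2 histories are equally likely in this model. Changing the baseline changes which women are counted, not how many.

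**Step 3. Scale at the planned size.** SAP 4.1: 450 × 0.80 = 360 completers, and 360 × 0.80 = 288 entrants, which reproduces the plan's figure. Assuming equal entry by arm, 288 / 3 = 96 women come from placebo, and 96 / 2 = 48 fall in each Placebo / linzagolix group.

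- Under the model: 48 × 10.1% × 9.3% = 0.45 woman per parameter per group at correlation 0.4, and 48 × 4.9% × 19.5% = 0.46 at 0.8. That is about 0.5 woman removed, and on average as many added.
- Without the model, for row 1 only: assume 1% to 10% go from Normal to High on placebo and 25% to 100% of those stay High. Then 48 × 0.01 × 0.25 = 0.1 to 48 × 0.10 × 1 = 4.8 women per group.

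Actual numbers are not given; SAP 1.2 says only that they were substantially below target.

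**Step 4. Is the missing summary available elsewhere?** Not from a listed table. Under SAP 4.2.10, an unscheduled value enters a by-visit summary only when the planned visit has no assessment, so an unscheduled peak usually does not reach the by-visit Baseline 2 shifts. As titled, "Table 14.4.4.5 Chemistry Parameters Shifts from Baseline 2" duplicates 14.4.4.3, so the Baseline 2 normal-range shift required by 4.8.4 has no table. The same duplication occurs at 14.4.2.5, 14.4.3.5 and 14.4.5.11.

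**The case against.** The liver-test sentence says the evaluation of shifts is to be extended, and the paragraph before it covers both baselines. The grammar of the sentence is broken, so Baseline 2 may simply have been dropped in editing. That reading is possible, but the text does not state it, and the following paragraph names both baselines again.

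The main baseline is also a legitimate reference. Protocol 13.5 adopts it for the extension. From it, all four groups have the same elapsed time to each visit, whereas Baseline 2 would set roughly 24 weeks in switchers against roughly 48 in continuers. Background rises in the continuing groups during Months 0 to 6 are attributed to linzagolix as well. This stands, and it is a reason to show both shifts rather than replace one with the other.

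Much is covered elsewhere. Chemistry shifts from Baseline 2 are specified for every visit, visits are monthly, and all laboratory data are listed. Women who met the hepatic discontinuation criteria are excluded (Protocol 9.2.2), so mainly smaller elevations are at issue, although Protocol 10.2.1.1 allows entry before Month 6 results are back. No hypothesis tests are planned, and the repeated table titles look like a clerical slip. All of this limits the impact. It does not supply the worst-value shift from the pre-drug value.

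A reader might go further and infer that liver shifts in the switching groups are overstated, or that half of them predate the drug because half of the time from main baseline to Month 12 is spent on placebo. The documents support neither. The first ignores the women missed in the other direction, and the second is a ratio of days, not of events.

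**Conclusion.** The omission is real and worth correcting, with modest impact. As written, the worst on-treatment liver-test shift can class a persistent placebo-period rise as new on linzagolix, and can miss a new rise in a woman who was High at main baseline but Normal before her first active dose. The fault lies in the attribution of individual women. No net inflation of the rate is shown.

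The size rests on assumptions. In the exchangeable model it is about 0.5 woman per parameter per group in each direction at planned enrolment. Row 1 alone could range from 0.1 to 4.8 women under the wider assumed rates. With the lower actual enrolment the expected counts are smaller, but in a small group one misclassified woman visibly moves a percentage.

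**What to change.** 1. In the liver-test sentence of SAP 4.8.4, add the shift from Baseline 2 for subjects on placebo in the main study, and present it beside the shift from main baseline.
2. State that, for these women, on-treatment values are those taken after the first extension dose, so that the Month 6 pre-dose sample is not counted.
3. List the worst-value liver-test shift table in Appendix B, which currently has none.
4. Retitle Tables 14.4.2.5, 14.4.3.5, 14.4.4.5 and 14.4.5.11 from clinical findings to normal ranges, so that the Baseline 2 shifts required by 4.8.4 are produced.

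The cost is a few lines of SAP text, one table with a Baseline 2 block, and four title corrections. Baseline 2 is already defined for these women, and no further data collection is needed.

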10.4.8 Laboratory parameters

Haematology, coagulation parameters and chemistry will be assessed at each visit during the Treatment Period, as well as at Month 1 ExFU and Month 3 ExFU visits. Fasting lipids will be assessed at Month 9, Month 12 and Month 3 ExFU visits.

E2, P4 and LH will be assessed at each visit during the treatment period, as well as at M1 ExFU and M3 ExFU visits. Serum levels of SHBG will be assessed at Month 9 and Month 12 visits.

Overnight fasting is required for Months 9, 12 and Month 3 ExFU visits.

Blood samples will be analyzed by the central laboratory. Details of blood sampling process, sample handling and shipment are described separately in a laboratory manual provided by the central laboratory. Central laboratory reference ranges will be filed in the investigator site file and in the trial master file. All laboratory results except E2, P4, LH and SHBG levels will be assessed by the Investigator/sub-Investigator. Clinically significant abnormalities compared to main study baseline status will be reported as AEs in the eCRF. E2, P4, LH and SHBG levels will not be communicated to keep the operational team and the sites blinded to treatment administration.

The laboratory parameters are listed in Appendix M.

There may be some additional laboratory parameters to be analysed as requested by the medical monitor in order to follow-up on existing abnormalities.

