## 4.2.5. Multiple Comparisons/Multiplicity

No formal hypothesis tests are planned for this extension study. Data will be summarized by timepoint for each treatment group.

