# Cytel

## Statistical Analysis Plan

Sponsor:	ObsEva		
Protocol:	19-OBE2109-00	5	
Document Version No.:	1.0	Document Date:	18-MAY-2021

- LDL ≥ 190 mg/dL
- HDL < 40 mg/dL

will be reported at each visit.

Shift tables from baseline and shift tables from baseline 2 (only for the subjects who are in the placebo arm in the main study) to each visit will be provided for the following LDL and Triglycerides categories (after rounding to integer values if necessary).

LDL:

- 0: ≤ 130 mg/dL
- 1: 131 to 159 mg/dL
- 2: 160 to 189 mg/dL
- 3: ≥ 190 mg/dL

Triglycerides:

- 0: ≤ 150 mg/dL
- 1: 151 to 300 mg/dL
- 2: 301 to 500 mg/dL
- 3: 501 to 1000 mg/dL
- 4: >1000 mg/dL

All laboratory data will be provided in data listings. Day 1 Serum levels of the anti-müllerian hormone (AMH) and fasting glucose will be included in the listings.

A subset listing will be presented for all abnormal clinically significant laboratory values.

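### The worst-on-treatment rule takes the highest value for albumin too, so in that summary a Low albumin is hidden unless all of the subject's on-treatment values are Low

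*SAP*

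**What the plan says.** SAP 4.8.4 (Laboratory Data) first plans shifts from baseline for haematology, coagulation, chemistry and lipids "to all visits according to the normal ranges with categories" Low, Normal and High. It then adds a rule for one group: "For Liver Function Test (LFT) parameters (ALT, AST, ALP, total bilirubin, direct bilirubin, indirect bilirubin, GGT, LDH, albumin and Creatine Kinase"). For these ten parameters the evaluation of shifts "will be extended by the worst (highest) on-treatment value (including unscheduled assessments"), again in Low/Normal/High. One direction is given for all ten, and no other part of the SAP gives albumin a different one.

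Albumin belongs to the blood chemistry panel (Protocol Appendix M), and Protocol 10.4.8 states: "Haematology, coagulation parameters and chemistry will be assessed at each visit during the Treatment Period". The output list in SAP 7.2 has no separate liver-test table. The nearest planned output is "Chemistry Parameters Shifts from Baseline Based on Normal Ranges from Month 7 up to Month 6 Extension Follow-up", which the worst-value rule would presumably feed. SAP 4.8.4 also says: "All laboratory data will be provided in data listings". The analysis is descriptive throughout; SAP 4.2.5 states: "No formal hypothesis tests are planned for this extension study".

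**The concern.** For ALT, AST, bilirubin and the enzymes on the list, a high value is the unfavourable one, so equating worst with highest works. Albumin is on the list as a liver-function marker, and there the unfavourable direction is low. A programmer who follows the text will code the maximum for all ten parameters and so report each subject's best albumin under the label of worst.

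It looks like an oversight. Later in the same section the lipid categories respect direction: LDL is flagged at or above 160 and 190 mg/dL, HDL below 40 mg/dL.

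What is at stake is the worst-case summary for albumin. Such a summary exists to catch an abnormality that comes and goes between visits, and this is also where SAP 4.8.4 explicitly brings in unscheduled values. After early termination SAP 1.2 makes safety the focus of the analysis, so a safety row that shows the opposite of its label is worth correcting.

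**Working it through.** The plan states no figure to reproduce, and sample size, power and alpha play no part. The check is a logical one on the derivation rule.

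**Inputs.** The ten parameters, the highest-value rule and the three categories come from SAP 4.8.4. A completer has six scheduled extension visits on treatment, Months 7 to 12 (Protocol 10.4.8 and Appendix A). The documents give no frequency of low albumin.

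**Step 1: when does the rule show Low?** Let a subject have k on-treatment values, each Low or Normal. There are 2^k − 1 sequences with at least one Low. The maximum is Low only if all k values are Low, which is 1 sequence. The minimum is Low in all 2^k − 1.

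| k | Sequences with at least one Low | Shown Low, highest rule | Shown Low, lowest rule |
|---|---|---|---|
| 1 | 1 | 1 | 1 |
| 2 | 3 | 1 | 3 |
| 3 | 7 | 1 | 7 |
| 6 | 63 | 1 | 63 |

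With six values the highest rule hides the Low in 63 − 1 = 62 sequences. With a single value the two rules agree.

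**Step 2: illustration in subjects.** Assume a per-visit probability p of Low and six values. If visits were independent, the lowest rule would show Low in 1 − (1 − p)^6 of subjects and the highest rule in p^6:

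- p = 5%: 26.5% against 0.0000016%
- p = 10%: 46.9% against 0.0001%
- p = 20%: 73.8% against 0.0064%

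Independence is the extreme case. If a subject's values were all Low or all Normal, both rules would show exactly p (5%, 10% or 20%) and nothing would be hidden. The truth lies between, and the documents do not say where.

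**Step 3: unscheduled values.** Under SAP 4.2.10 (Other safety data), an unscheduled assessment is assigned to a planned visit if it lies within ±14 days of the theoretical date, the test was planned there, and the visit has no result of its own. Setting this beside SAP 4.8.4 gives two cases:

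- The scheduled result is missing: the unscheduled Low is assigned to the visit and appears in the by-visit tables.
- The scheduled result exists: the unscheduled Low is not assigned. It could be tabulated only through the worst-value summary, and the highest rule hides it there if any on-treatment value is Normal or High.

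Extra draws are foreseen: Protocol 10.4.8 lets the medical monitor request additional laboratory parameters to follow up abnormalities.

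**The case against.** The best defence is that almost nothing is lost. Low/Normal/High shifts are planned at every visit. SAP 4.2.1 includes the minimum among the descriptive statistics, so the lowest albumin at each visit in each group is tabulated. Shifts by clinical significance, full listings and a subset listing of clinically significant values complete the picture. The study is descriptive and much smaller than planned. The liver withdrawal criteria in Protocol 10.7.2.1 rest on ALT, AST, bilirubin, INR, symptoms and eosinophilia, not on albumin. All of this stands and is why the point is minor. None of it makes the highest albumin the worst one.

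Stronger readings are tempting, but the documents do not support them:

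- A reader might infer that a low albumin can never appear as the worst value. It does appear when all of a subject's values are Low or her only value is Low. Short follow-up is plausible, since SAP 2.1 includes subjects whatever their treatment duration.
- A reader might infer that the rule misclassifies every fall in albumin. A fall within the normal range is Normal under either rule; the rules differ only when Low and non-Low values are mixed within one subject.
- A reader might infer that the worst-value summary is the only tabulated place for unscheduled values. SAP 4.2.10 assigns some of them to visits.
- A reader might look for a dedicated liver-test table with this defect. SAP 7.2 lists none.

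**Conclusion.** The rule is wrong as written for one of the ten listed parameters. In the worst-value shift from baseline, a Low albumin is hidden unless all of the subject's on-treatment values are Low: 62 of 63 six-visit Low/Normal patterns containing a Low, 6 of 7 with three values, 2 of 3 with two, and none with one. How many subjects this affects cannot be derived from the documents.

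The impact is confined to this descriptive summary. Low values at scheduled visits remain visible elsewhere. The one gap in the tables is a Low seen only at an unscheduled draw when the scheduled visit already has a result; that value would appear in the listings alone.

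The conclusion rests on two assumptions: that albumin is listed as a liver marker, so that low is its adverse direction, and that the programmer applies the highest-value rule to every parameter named. Severity: a useful correction, not a threat to the study's conclusions.

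**What to change.** In SAP 4.8.4, state that the worst on-treatment value is the lowest for albumin and the highest for the other nine listed parameters. Showing both the lowest and the highest albumin would serve equally well. It would also help to name in SAP 7.2 the table that carries the worst-value shift, since none is identified there now.

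The cost is one phrase in the SAP and one line of code. No new data are needed, no other output changes, and there is no statistical downside.
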